#### **4.3 Resistance Training Program**

Participants will follow the same periodized, resistance training program for 6 weeks. The program will consist of three sets of 6, 8, 10 repetitions to muscle fatigue in order. Resistance training will start on the first day of supplementation and will consist of a split routine involving whole body musculature. Day 1 will involve chest and biceps musculature and include the following exercises in order: machine-based chest press, free weight incline bench press or dumbbell press, free-weight flat dumbbell press, machine-based pec-dec, free-weight standing barbell curl, free-weight alternate arm dumbbell curl and machine-based preacher curl. Day 2 will involve leg and core musculature and include the following exercises in order: free-weight squat, machine-based leg press, machine-based leg extension, machine-based leg curl, machine-based calf raise, and

machine-based weighted abdominal crunches. Day 3 will serve as a rest day from training. Day 4 will involve back and triceps musculature and include the following exercises in order: body weight or weight-assisted chin-ups, machine-based seated row, machine-based lat pull-down, free-weight alternate dumb-bell row, free-weight close-grip bench press, machine-based cable triceps bar extension, and machine-based cable triceps rope extension. Day 5 will involve shoulder and core musculature and include the following exercises in order: free-weight dumbbell press, free-weight upright row, free-weight shrugs, free-weight or machine based lateral deltoid flys, free-weight or machine-based rear deltoid flys and machine-based weighted abdominal crunches. Day 6 will serve as a rest day from training. This cycle will be repeated for 6 weeks. Participants will maintain training logs to ensure adherence and compliance to the study and to determine total training volume (load x repetitions x sets).

#### **4.4 Primary Dependent Variables**

##### **4.41 Muscle thickness**

Muscle thickness (right side) of the elbow and knee flexors and extensors will be measured using B-mode ultrasound (LOGIQ e, GE Medical Systems) in the Exercise Physiology Laboratory, University of Regina. To measure elbow flexor and extensor muscle thickness, a small mark will be drawn on the lateral side of the arm to indicate 65% of the distance down from the acromion process to the olecranon process. A tape measure will be wrapped around the arm at the 65% mark and used as a reference, while another mark will be placed on the bulk of the biceps and triceps where the center of the ultrasound probe will be placed. To measure elbow flexor muscle thickness, each participant will place their right arm flat on a table with the belly of the biceps facing upwards and the forearm supinated. To measure elbow extensor muscle thickness, participants will stand with their back facing the researcher and elbows relaxed and extended.

To measure knee flexor and extensor muscle thickness, a small mark will be drawn on the lateral side of the leg to indicate 70% of the distance down from the greater trochanter to the lateral epicondyle of the tibia. A tape measure will be wrapped around the leg at the 70% mark and will be used to mark another reference point on the bulk of the vastus lateralis (knee extensor) and biceps femoris (knee flexor) where the center of the ultrasound will be placed. To measure knee extensor muscle thickness, each participant will be placed on a table in a seated position with the leg extended and relaxed. To measure knee flexor muscle thickness, each participant will be prone on the table with both legs extended and relaxed.

Precise markings using a permanent marker will be made on a transparency film sheet to ensure that the exact identical site is measured before and after the resistance training program by the same researcher. Water-soluble transmission gel (EcoGel 200, Eco-Med Pharmaceutical Inc., Mississauga, Ontario, Canada) will be placed on the measurement site to provide acoustic contact with the surface of the muscle. An 8-MHz scanning transducer head will be placed perpendicular to the muscle area. When the image is produced on the screen, the image on the monitor will be frozen. With the image frozen, a cursor will be enabled to quantify muscle thickness (cm) at three sites: proximal, mid and distal, as determined by divisions (1cm) on the monitor. Muscle thickness measurements will be determined from the monitor screen by measuring the distance from the bottom of the subcutaneous adipose layer to the surface of the humerus for the elbow flexors and extensors and to the surface of the femur for the knee flexors and extensors. Three muscle thickness measurements will be taken at each of the four muscle group sites. The values at each of three sites will be averaged to quantify one muscle thickness value that will be used for analysis.

The same researcher will perform all measurements. The reproducibility (coefficient of variation; intraclass correlation coefficient) of muscle thickness measurements will be determined

prior to supplementation and training by assessing 10 participants, > 24 hours apart. Baseline and post-testing muscle thickness measurements will be performed prior to assessing 1-RM strength and endurance. Post-testing muscle thickness measurements will be performed  $\geq$  48 hours after the last resistance training session.

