#### **4.2 Research Design**[L][SEP]

The study will be a double-blind, repeated measures design. In order to minimize group differences, participants will be matched according to age and weight and be randomized on a 1:1:1:1 basis to one of four groups: Creatine + Caffeine (CR-CAF; 0.1 g/kg of creatine monohydrate powder + 3 mg/kg of caffeine [micronized powder]); Creatine (CR; 0.1 g/kg of creatine monohydrate powder + 3 mg/kg of caffeine placebo [micronized cellulose powder]), Caffeine (CAF; 3 mg/kg of caffeine + 0.1 g/kg of creatine monohydrate placebo [maltodextrin]) or placebo (PLA; 0.1g/kg creatine monohydrate placebo + 3 mg/kg of caffeine placebo). An individual, blinded to supplement and group allocation, will be responsible for the preparation of study kits. Each study kit will contain the participants supplement for the duration of the study, detailed supplementation instructions, measuring spoons, supplementation compliance log, daily caffeine consumption log and a resistance training log. Supplement powders will be similar in energy content, color, taste, texture, and appearance. The creatine dosage of 0.1 g/kg has previously been shown to be effective for increasing muscle mass and muscle performance. The caffeine dosage of 3 mg/kg has been shown to increase muscle performance. Participants will be instructed to refrain from additional caffeine sources  $\geq 3$  hour prior to consuming their supplement so that a valid estimate regarding the effects of caffeine supplementation on muscle can be made. On training days, participants will mix their supplement powder in water and consume the solution 60 minutes prior to exercise. Sixty minutes was chosen because this is the approximate time it takes for peak plasma caffeine concentrations to occur after caffeine ingestion and pre-exercise

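### Muscle thickness is read by hand on the scanner by an operator who knows the visit, so its pre-post effect sizes are open to expectation bias; the blinded group comparison is not affected (minor, cheap to improve)

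*Protocol*

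**What the plan says.** Protocol 4.41 describes a manual reading made at the scanner. The image is frozen, and then: "With the image frozen, a cursor will be enabled to quantify muscle thickness (cm) at three sites: proximal, mid and distal". The reading is made on screen, as the distance between the lower edge of the fat layer and the bone: "Muscle thickness measurements will be determined from the monitor screen". One person does this throughout: "The same researcher will perform all measurements". Sites are mapped on a transparency film, "to ensure that the exact identical site is measured before and after the resistance training program by the same researcher". No step saves the images for later reading or masks the reader to the visit.

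On blinding, 4.2 states: "The study will be a double-blind, repeated measures design". It names the kit preparer as blinded but does not mention the ultrasound operator separately. Participants are "randomized on a 1:1:1:1 basis to one of four groups", and under 4.3 all of them follow the same 6-week training programme.

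Protocol 4.5 fits a 4 (group) x 2 (time) repeated measures ANOVA and follows a significant interaction with a one-factor ANOVA on change scores. For significant main effects and interactions it reports Cohen's d, defined as post-training mean minus pre-training mean over the pooled pre-training SD. A d below 0.20 is called trivial and 0.20 to 0.49 small.

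**The concern.** Blinding to supplement hides the group but not the visit. That the operator knows the visit is an inference, but a safe one, because the baseline film is used to find the site again at post-test. A reader who expects muscle to grow over 6 weeks of training can, without intending to, place the cursor a little wider at post-test. All four thickness variables, which belong to the primary dependent variables, depend on this step.

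The planned reproducibility check would not reveal such a shift. It measures 10 participants twice before supplementation and training start, so neither reading is made in the expectation of growth. At stake are the time main effect for thickness and the d values computed from post minus pre.

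**Working it through.** **1. The plan's own figure.** The sample size of 48 in 4.1 reproduces. For the within-between interaction, lambda = f² x N x m / (1 - rho), with f = 0.25, N = 48 and m = 2 from the protocol, and rho = 0.5 assumed (not stated). This gives lambda = 0.0625 x 48 x 2 / 0.5 = 12. With 3 and 44 df and alpha 0.05, power is 0.803. Nothing below changes this figure.

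**2. Where a reading shift goes.** Let B be a post-visit over-reading that is the same in all groups, and D_g the true mean change in group g.
- Observed change in group g: D_g + B.
- Difference between groups g and h: (D_g + B) - (D_h + B) = D_g - D_h. B cancels.
- Time main effect: mean of D_g, plus B. B enters in full.
- Reported d: (post - pre + B) / SD = true d + B/SD. B enters in full, including where a group's d accompanies a significant interaction, because 4.5 defines d as a pre-post quantity.

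**3. Effect on d.** The protocol gives no reading error and no SD for thickness. Assumed: B = 0.5 to 1.0 mm, SD = 4 mm.
- 0.5 / 4 = 0.125
- 1.0 / 4 = 0.25

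Against the 0.20 cut-off in 4.5:
- A shift of 0.125 alone stays trivial. It crosses only if the true d is already at least 0.20 - 0.125 = 0.075.
- A shift of 0.25 crosses even from a true d of 0.
- The shift alone reaches the cut-off when B = 0.20 x 4 = 0.8 mm.

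Because 4.5 computes d for significant effects, the crossing is reported only if the effect is also significant.

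**4. Effect on the test of time.** Assume no true change, N = 48, a bias b in SD units common to all groups, and a pre-post correlation rho (not in the protocol). Then lambda = N x b² / (2(1 - rho)) with 1 and 44 df. Example: b = 0.25, rho = 0.5 gives 48 x 0.0625 / 1 = 3.0. The probability of a significant time effect (nominally 5%) is:

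| b (SD) | rho = 0.5 | rho = 0.8 | rho = 0.9 |
|---|---|---|---|
| 0.10 | 10% | 19% | 33% |
| 0.125 | 13% | 27% | 47% |
| 0.20 | 27% | 57% | 86% |
| 0.25 | 40% | 76% | 97% |
| 0.30 | 53% | 90% | 99.5% |

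**5. Effect on the group-by-time test.** This was checked in 20,000 simulated trials of 4 x 12 participants at rho = 0.5. With a common bias of 0.1, 0.2 or 0.3 SD the rejection rate is 5.0%, 4.8% and 4.9%, so the test is not affected. If the bias occurs in the two creatine groups only, the rate is 7.6% at 0.2 SD, 11% at 0.3 SD and 26% at 0.5 SD. That case requires the operator to know or guess the group.

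**The case against.** The strongest objection is that this does not touch the trial's question. The study compares supplements, it is declared double-blind, and expectation of growth at every post visit moves all four groups alike. This stands, and it is why the point is minor.

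A second objection is that the time effect cannot be read as a training effect in any case, since every group trains and none is untrained. This also stands. Masked reading would leave the effect mixed with anything else that changes over 6 weeks.

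A third is that masked reading does not deal with acquisition. Probe pressure, probe angle and the choice of frame to freeze remain with an operator who knows the visit. This stands too: the remedy reduces the bias and no more.

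A reader might go further and infer that the supplement comparison itself is biased, since 4.2 asks participants at the end what they thought they received. The documents do not support this. That question checks participant blinding; it is no evidence that the operator is unblinded or reads the groups differently. That 4.2 does not name the operator as blinded is a gap worth closing, not a sign that blinding fails.

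Finally, one operator, film-mapped sites and averaged readings form a coherent procedure. They control random error well, but not a shift tied to the visit.

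**Conclusion.** The point holds as a minor one. Thickness is read by hand by someone who knows the visit, so the time main effect and the pre-post d values for thickness are open to expectation bias in cursor placement. The group-by-time comparison is unaffected as long as the operator is blinded to group.

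The size cannot be established from the protocol. Under an assumed shift of 0.5 to 1.0 mm and an SD of 4 mm, d moves by 0.125 to 0.25. This changes the label from trivial to small only at the upper end of that range, or when the true d is already near 0.20. The false-positive rates for time also rest on assumed correlations. They show that the test is sensitive to such a shift, not that a shift will occur. Sample size, alpha and the planned tests stay as they are.

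**What to change.** In 4.41, save each frozen image unmeasured under a coded file name. After the last post-test, have the same researcher measure all pre and post images in random order, masked to participant, visit and group. State in 4.2 that the ultrasound operator is blinded to group. In 4.5, add that the time effect on thickness will be interpreted with caution: image acquisition remains unmasked, and with no untrained group it is not a pure training effect.

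The cost is image storage, coding of the files and some hours of the same researcher's time, with no extra scan or staff. The downside is that thickness values are not available on the visit day. The change also gives the group comparison some protection should operator blinding leak.

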#### **4.42 Muscular Strength and Endurance**

Machine-based leg press and machine-based chest press 1-RM will be performed in the Exercise Physiology Laboratory, University of Regina. To determine the 1-RM, participants will perform a 5-minute warm-up on a stationary cycle ergometer at a self-selected intensity and light passive stretching. Participants will then perform two warm-up sets of each exercise in the following order: 1 set of 10 repetitions using a load, which will be determined by each participant to be comfortable, and 1 set of 5 repetitions using a heavier weight. Two-minutes after the warm-up sets, the load will be progressively increased for each subsequent 1-RM attempt. Participants will rest (passively) for 2 minutes between 1-RM attempts. Participants will reach their 1-RM in  $\leq$  6 sets. To determine muscle endurance, participants will perform repetitions to volitional fatigue (1 set) using 50% baseline 1-RM for the squat and chest press.

To measure leg press 1-RM and endurance, participants will be positioned in a vertical leg press machine with both feet pushing up against the machine. Following a demonstration, participants will be instructed to lower the weight until an internal angle at the knees of  $90^\circ$  is achieved before returning to the upright position. The reproducibility (coefficient of variation; intraclass correlation coefficient) of leg press 1-RM will be determined prior to supplementation and training by assessing 10 participants, > 24 hours apart.

For chest press 1-RM and endurance, participants will be positioned in the bilateral chest press machine with both feet placed on the floor. Following a demonstration, participants will be

instructed not to lift their hips off the bench or arch their back during the lift. Participants will be instructed to grasp the bars (overhand grip) approximately shoulder width apart and push the load away from the body until full extension without locking the elbows and then lower the load back to the starting position. The reproducibility (coefficient of variation; intraclass correlation coefficient) of chest press 1-RM will be determined prior to supplementation and training by assessing 10 participants, > 24 hours apart.

Muscle strength and endurance will be assessed in order: (a) leg press strength, (b) chest-press strength, (c) leg press endurance, and (d) chest-press endurance. Five minutes of rest will separate each test. Muscle strength and endurance determination will be separated by 10 minutes of rest. Post-testing strength and endurance measurements will be performed  $\geq 48$  hours after the last resistance training session.

#### **4.43 Diet**

Dietary intake will be recorded during the first and final week of supplementation and resistance training to assess differences in total energy and macronutrient composition between groups. Participants will use a 3-day food booklet to record food intake for two weekdays and one weekend day. Participants will be instructed to record all food items, including portion sizes consumed for the three designated days. My FitnessPal will be used to analyze 3-day food records.

#### **4.44 Adverse Event Assessment**

In the case of an adverse event, participants will be asked to complete an adverse event form in order to provide details on the type of adverse event, the severity (i.e. mild, moderate, severe, or life threatening), the frequency, and the relationship to the intervention (i.e. not related, unlikely, possible, probable, or definite).

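### Section 4.44 has participants rate the severity and cause of their own adverse events on an event-triggered form, with no study-team rating or routine enquiry described

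*Protocol*

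**What the plan says.** Section 4.44 of the protocol is a single sentence and is the only text on adverse events. The trigger is the occurrence of an event, and the section names who fills in the form: "participants will be asked to complete an adverse event form in order to provide details on the type of adverse event, the severity". Severity is graded on four levels, and how often the event happened is recorded too. A separate item on the same form asks for "the relationship to the intervention (i.e. not related, unlikely, possible, probable, or definite". The participant is therefore asked for a four-level severity grade and a five-level causality rating. The section gives no criteria for either scale.

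Section 4.2 sets the blinding: "The study will be a double-blind, repeated measures design". The same section places the outcome measurements at baseline and after the intervention and describes no visit between them.

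**The concern.** Two features of the stated method weaken the safety data.

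The first is who rates. A participant can say what he felt, when, how often and how strongly. Whether the supplement caused it is a comparative judgement, which needs knowledge of the alternatives and the same standard applied to every participant. With up to 48 raters, each judging only his own events and without criteria, a label such as probable need not mean the same thing from one participant to the next.

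The second is when events are collected. The form is completed if an event arises, and no standard question to all participants is described. Mild events are the ones most easily left unmentioned under such a scheme.

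At stake is any later statement about how well the supplements, alone or together, were tolerated.

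**Working it through.** The protocol gives no figure on adverse events to reproduce, so the check is mainly a comparison of sections, with two small sums.

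**1. Who rates.** In Section 4.44 the participant completes the form, and severity and relationship are both items on it. No other section assigns either rating to the investigator or to any other member of the team.

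**2. How hard the causality judgement is.** The protocol itself supplies competing explanations for the same symptom:
- Section 4.1 admits habitual caffeine users and notes that withdrawing from caffeine can bring adverse symptoms.
- Section 4.2 restricts other caffeine only in the hours before the supplement (at least 3), so habitual intake continues around it.
- Sections 4.2 and 4.3 place the supplement 60 minutes before training sessions whose sets are taken to muscle fatigue.

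A participant with, say, a headache or a racing heart after a session has at least three candidate causes and does not know which supplement he received.

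**3. How many occasions there are for events, and when they are asked about.** Section 4.3 gives a 6-day cycle with 4 training days, repeated for 6 weeks. Section 4.2 gives the supplement on training days only.
- Days: 6 × 7 = 42
- Cycles: 42 / 6 = 7
- Supplemented sessions per participant: 7 × 4 = 28

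Over these roughly 28 sessions the document describes no scheduled enquiry about events, and none at the post-test visit.

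**4. What one participant is worth.** Section 4.1 gives 48 participants and Section 4.2 allocates them equally to four groups.
- Per arm: 48 / 4 = 12
- One participant: 1 / 12 = 8.3 percentage points

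One event that is missed, or rated differently by another standard, thus moves an arm's rate by 8.3 points. The step follows from the arm size alone and says nothing about how often such an error would happen.

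**5. What depends on it.** The primary variables in Sections 4.2 and 4.4 are muscle thickness, strength and endurance. Section 4.5 analyses these together with diet, baseline data and training volume. It describes no adverse event comparison, so no efficacy result depends on the ratings.

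**The case against.** The strongest reply is that Section 4.44 is brief rather than wrong. It says that the participant provides details, not that his rating is final, and it does not exclude review by the investigator. Consent and contact pages are not in the text at hand and may carry reporting instructions. Adverse events are neither a primary variable nor part of the stated analysis. A blinded team member does not know the allocation either, and could guess it from stimulant symptoms as a participant could.

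Much of this stands. It limits the point to what Section 4.44 assigns and to a risk of under-recording, and it keeps the point minor. It does not remove the point. Who rates causality and how events are elicited are matters of conduct, and the protocol has placed the rating with the participant. A single blinded rater brings expertise and one standard, even though guessing remains possible.

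Four stronger readings are tempting, and the document does not support them:
- **The form is not supplied to participants.** The kit list in Section 4.2 ("Each study kit will contain the participants supplement for the duration of the study, detailed supplementation instructions, measuring spoons" and three logs) omits it, but the list is not said to be complete. The food booklet that participants use under Section 4.43 is missing from it too. Staff may hand out the form when an event is reported.
- **The participant is the sole and final assessor.** He is the only one described. The text does not go further.
- **Ratings will follow the participant's guess at his group.** Section 4.2 asks for that guess at the end, so guesses are expected, but nothing shows that they drive the event ratings.
- **A given share of events is lost.** The document gives no reporting rate, so no figure for lost events can be derived.

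**Conclusion.** The point holds as a minor one about safety data. Section 4.44 assigns severity and causality to the participant, ties recording to the occurrence of an event, and describes neither a rating by the study team nor a routine enquiry. The likely result is inconsistent causality ratings and some risk of missing mild events. In arms of 12, where each participant counts for 8.3 percentage points, a tolerability statement built on such data would be weak.

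This rests on three assumptions: that Section 4.44 describes the whole procedure, that the four arms are filled equally and all 48 participants are retained, and that the trial will report on tolerability at all. If the team already reviews and rates each event, one added sentence closes the first half of the point. The primary outcomes and their analysis are unaffected.

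**What to change.** In Section 4.44:
1. Have the participant describe the event, its timing, its frequency and how intense he found it.
2. Have a blinded member of the existing study team assign the severity grade and the relationship to the intervention, using the scales already listed.
3. Ask every participant one standard open question about adverse events at the existing post-test visit, and record the answer whether or not a form was completed earlier.

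This costs a few minutes of existing staff time per participant or event, with no added visit or staff. Two limits remain. Blinded rating improves consistency but does not fully prevent the rater from guessing the allocation. A question at the end relies on recall over 6 weeks, so it recovers events that were not volunteered but not those that were forgotten.
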